1.1 Description of the proposed project

The purpose of this study is to compare two techniques for treating hemorrhoids, the ligation and hemorrhoidopexy technique and the conventional ligation of hemorrhoidal arteries using ultrasound, in patients with non-complicated hemorrhoids.

2. INTRODUCTION

2.1 Literature

Surgical operations for the treatment of perianal diseases are a major part of all elective surgical cases. The reduction in the hospitalization time of patients undergoing surgical procedures for benign perianal diseases is to the benefit of both the patient and healthcare provider¹. The importance of 'one day' surgical operations lies in the fact that the patient returns directly to his social and working environment, while the number of occupied hospital beds and the total hospitalization costs are reduced. A typical example is the goal set by NHS, where the 75% of the scheduled operations should consist of 'one day' operations¹. In order to achieve this goal, several obstacles should be dealt with, including the implementation of more efficient and safe surgical techniques. Therefore, this would be associated with a decrease in the operation time, early recovery and faster hospital discharge.

Hemorrhoids is one of the most common benign perianal diseases. According to a recent prospective study² of 976 patients, 38.93% of them suffered from hemorrhoids, with 8.16% and 0.53% being Grade III and IV, according to Goligher classification, respectively. The percentage of the symptomatic patients was, also, significant (44.74%). Symptomatic hemorrhoids, includes bleeding, pruritus, pain, poor hygiene and the presence of palpable hemorrhoid nodules.

As far as the blood supply of the rectum and the broader anatomic region is concerned, it is provided by the superior, middle and inferior hemorrhoidal arteries. The superior hemorrhoidal artery is a branch of the inferior mesenteric artery and is carried behind the rectum, where it provides branches up to the internal sphincter muscle. The right and left middle hemorrhoidal artery originate from the respective internal iliac artery and their branches are cross-linked with the respective branches deriving from the superior hemorrhoidal artery. Finally, inferior hemorrhoidal arteries derive from the respective internal pudendal arteries. Correspondingly, hemorrhoidal venous plexus consists of the middle and inferior hemorrhoidal veins, which through the internal iliac veins drain into the inferior cava vein. Hemorrhoidal tissue constitutes a continence mechanism of the upper rectum and consists of vascular tissue, connective tissue and smooth muscle fibers, within the rectal canal. Through the approximation of the hemorrhoidal tissue, closure of the anal canal and protection of the sphincter mechanism is achieved. Since modern pathogenesis theories of hemorrhoids attribute to the increased arterial flow in the hemorrhoidal plexus the generating cause of this disease, recent anatomical studies mapped the vascular network, indicating that the arteries are not confined to the anatomical regions described in the literature³.

According to recent guidelines⁴, the modification of dietary intake, through the increase of fluid and fiber intake, consists the first line treatment of symptomatic hemorrhoids. However, in Grade III-IV hemorrhoidal disease or in Grade II, where conservative therapy failed, surgical intervention is required. Surgeon has plenty of techniques at his disposal, in order to treat hemorrhoids. Examples of these techniques are operations, such as hemorrhoidectomy (open⁵, closed⁵, Milligan-Morgan⁶, Parks⁶, using staplers⁷, using energy sources, e.g. Harmonic⁸, Ligasure⁹, Laser¹⁰, bipolar forceps¹¹), elastic rings ligation¹², sclerotherapy¹³ and hemorrhoidal arteries ligation (HAL) or Transanal Hemorrhoidal Dearterialization (THD)¹⁴.

Ligation of hemorrhoidal arteries using a Doppler apparatus, is a minimally invasive technique that was first applied by Morinaga et al.¹⁵ in 1995 and has as principle the elective ligation of the arteries that supply the hemorrhoidal plexus. In a recent meta-analysis the superiority of HAL in areas such as, postoperative bleeding, emergency reoperation, operative duration, length of hospital stay and postoperative pain, was shown. A major drawback of this technique, however, remains the high rate of recurrence, which ranges from 11.1% to 59.3%, for Grade IV hemorrhoids¹⁷.

Despite the comparative advantages of this minimally invasive technique, the high cost of the necessary equipment and the respective consumables, is a barrier to its broad application. Gupta et al.¹⁸ in a prospective randomized study, compared Doppler-Guided HAL (DG-HAL) to hemorrhoid artery ligation and hemorrhoidopexy. Ligation was performed on the hemorrhoid nodule at the 3rd, 7th and 11th hours, followed by continuous hemorrhoidal nodule ligation and hemorrhoidopexy¹⁹. The DG-HAL group had a significantly longer operative time (31 min vs 9 min) and post-operative pain (4.4 vs 2.2), without any differences in complication or recurrence rates. Similarly, Huang et al.²⁰, reported a respective ligation technique, where, through the use of the index finger, the artery was palpated, followed by repeating compression and ligation cycles, in order to fix the affected hemorrhoids above the dental line. In this group, operative time was longer when compared to the DG-HAL group (35.57 vs. 12.73). There was no difference in terms of postoperative improvement of symptoms and hospitalization duration. In the experimental group, however, the cost of hospitalization and the relapse rate was significantly lower. Finally, Aigner et al.²¹, in a recent randomized study, investigated the efficacy of hemorrhoidopexy for Grade III hemorrhoids. They concluded that the techniques of hemorrhoidopexy are effective and the addition of DG-HAL does not affect the results.

Given these facts, the present trial was designed, in order to compare the two techniques for hemorrhoids treatment, the ligation and hemorrhoidopexy technique and the conventional ligation of hemorrhoid arteries using ultrasound.

2.2 Research Group Experience

In a prospective 4-year study with a total of 90 patients²², the immediate post-operative and long-term course of patients undergoing DG-HAL hemorrhoid artery ligation was investigated. Totally, 64.4% of the included patients was discharged from the hospital, within 24 hours of the operation, 4.4% of patients needed additional analgesic treatment in the next 24 hours, while only 6.6% developed disease recurrence, one year after the operation. Additionally, a prospective randomized study of our clinic, compared pudendal nerve block and local anesthesia in 120 patients who underwent ultrasound scissors hemorrhoidectomy. A statistically significant lower rate of additional postoperative analgesic treatment was observed in the pudendal nerve block, while the level of postoperative pain, calculated on the Visual Analogue Scale (VAS scale), on the operative day was higher in the group of local anesthesia (5.1 vs. 2.2 $p < 0.001$)²³.

3. RESEARCH PROTOCOL

3.1 Sample

The sample will consist of male and female patients aged 18 to 80 years, with an American Society of Anesthesiologists (ASA) score of I and II.

3.2 Diseases

Patients with Grade \leq III hemorrhoids, according to Goligher's classification, will be included.

3.3 Exclusion Criteria

The exclusion criteria include:

- Acute perianal diseases, such as perianal abscesses, complicated hemorrhoids (e.g., thrombosis) and acute anal fissure
- Malignant perianal disorders
- Patient age \geq 80 years
- ASA score III
- Presence of inflammatory bowel disease
- History of a previous rectoanal operation
- Presence of a clinically significant cardiovascular, respiratory, renal, hepatic or metabolic disorder. Furthermore, diseases, such as obesity, psychiatric disorders or gastrointestinal disorders constitute exclusion criteria.

3.4 1st Arm

The patient will be placed in the Lloyd-Davies position and having provided a sterile field, using a 10% povidone iodine solution, rectal dilatation will be performed with a 10% xylocaine gel, thus allowing the entrance of the proctoscope (THD America). The proctoscope will be combined with a Doppler sensor in order to detect the hemorrhoidal arteries and, also, a light source. Furthermore, a casing at the distal end of the apparatus that allows the proper placement and rotation of the needle-holder and a special window above the sensor and, thus, enables the placement of the ligations at the correct height and depth, through the capturing of the mucosa and the submucosa and the prevention of the perforation of the rectal wall. After the hemorrhoidal artery location, through the use of the ultrasound, Z ligations will be placed, using an absorbable polyglycolic acid suture (2-0, 5/8 inch needle). The proper artery ligation will be confirmed by the absence of the Doppler signal. In the presence of residual hemorrhoidal tissue, the upper part of the proctoscope will be removed and hemorrhoidopexy will be performed, by applying a continuous suture from the hemorrhoidal stem and peripherally. During hemorrhoidopexy, only the mucosa and the submucosa of the hemorrhoidal nodules, above the dental line, will be captured. At the end of the procedure, a hemostatic gauze will be placed in the surgical field. Prior to operation, the patients will be submitted to spinal anesthesia. Using an atraumatic 25 Gauge (G) needle, a levobupivacaine 5mg/ml and fentanyl 25mg solution, will be administered at the height of lumbar (L)2-L3 or L3-L4²⁴.

3.5 2nd Arm

In the experimental arm, the patient will be placed in the Lloyd-Davies position and having provided a sterile field, using a 10% povidone iodine solution, rectal dilatation will be performed with a 10% xylocaine gel, thus allowing the entrance of a conventional proctoscope, with an attached light source. After the identification of the hemorrhoidal nodules (3rd, 7th, 11th hour), their ligation, using an absorbable polyglycolic acid suture (2-0, 5/8 inch needle), will be performed. The location of the hemorrhoidal artery will be confirmed, through palpation, with the use of the index finger. Initially, a fixative suture will be placed in the hemorrhoidal nodule and then, using a continuous suture from the hemorrhoidal stem and peripherally, hemorrhoidopexy, will be performed. During hemorrhoidopexy, only the mucosa and the submucosa of the hemorrhoidal nodules, above the dental line, will be captured. At the end of the procedure, a hemostatic gauze will be placed in the surgical field. Prior to operation, the patients will be submitted to pudendal nerve block. Using an atraumatic 25 Gauge (G) needle, a 20ml lidocaine solution (diluted with saline in a 1:1 rate) will be administered bilaterally, medially to the ischial tuberosity²⁵. Ten minutes before the operation, the patient will receive 1-2.5mg midazolam and 0.1-0.2 mg fentanyl.

3.6 Primary endpoint

The primary endpoint of the present study, is the identification of difference in the symptoms remission rate, within one month postoperatively, between the ligation and hemorrhoidopexy technique and the conventional ligation of hemorrhoidal arteries using ultrasound, in patients with non-complicated hemorrhoids. If the symptoms are treated then it will be defined as=1 'YES' If the symptoms are not treated then it will be defined as=0 'NO'. The time frame will be 1 month postoperatively.

3.7 Secondary endpoints

The secondary endpoints of the present study are:

- Operative time. Measurement unit: minutes. Time Frame: Intraoperative period
- Postoperative mobilization time. Measurement unit: hours. Time Frame: Postoperative period up to hospital discharge. Maximum time frame 24 hours
- Postoperative pain level at 12 hours after surgery, quantified with the use of the VAS scale. Time Frame: 12 hours postoperatively
- Onset of oral feeding. Measurement unit: hours. Time Frame: Postoperative period up to hospital discharge. Maximum time frame 24 hours
- Difference in the rates of adverse effects during hospitalization:
 - Hypotension. Occurrence of postoperative hypotension. If such an episode occurs, then it will be defined as=1 'YES' If such an episode does not occur, then it will be defined as=0 'NO'. Time Frame: Postoperative period up to hospital discharge. Maximum time frame 24 hours

- Nausea. Occurrence of postoperative nausea. If such an episode occurs, then it will be defined as=1 'YES' If such an episode does not occur, then it will be defined as=0 'NO'. Time Frame: Postoperative period up to hospital discharge. Maximum time frame 24 hours
- Vomiting. Occurrence of postoperative vomiting. If such an episode occurs, then it will be defined as=1 'YES' If such an episode does not occur, then it will be defined as=0 'NO'. Time Frame: Postoperative period up to hospital discharge. Maximum time frame 24 hours
- Headache. Occurrence of postoperative headache. If such an episode occurs, then it will be defined as=1 'YES' If such an episode does not occur, then it will be defined as=0 'NO'. Time Frame: Postoperative period up to hospital discharge. Maximum time frame 24 hours
- Urinary retention. Occurrence of postoperative urinary retention. If such an episode occurs, then it will be defined as=1 'YES' If such an episode does not occur, then it will be defined as=0 'NO'. Time Frame: Postoperative period up to hospital discharge. Maximum time frame 24 hours
- Bleeding at the operative site. Occurrence of postoperative bleeding at the operative site. If such an episode occurs, then it will be defined as=1 'YES' If such an episode does not occur, then it will be defined as=0 'NO'. Time Frame: Postoperative period up to hospital discharge. Maximum time frame 24 hours
- Postoperative time that the patient can be safely discharged. Measurement unit: hours. Time Frame: Postoperative period up to hospital discharge. Maximum time frame 48 hours
- Complications occurring at 7 days postoperatively:
 - Pain on the basis of the VAS scale. Postoperative pain level at 7 days after surgery, quantified with the use of the VAS scale. Time Frame: 7 days postoperatively
 - Oedema at the operative site. Occurrence of postoperative oedema at the operative site. If such an episode occurs, then it will be defined as=1 'YES' If such an episode does not occur, then it will be defined as=0 'NO'. Time Frame: 7 days postoperatively
 - Hematoma at the operative site. Occurrence of postoperative hematoma at the operative site. If such an episode occurs, then it will be defined as=1 'YES' If such an episode does not occur, then it will be defined as=0 'NO'. Time Frame: 7 days postoperatively
 - Infection at the operative site. Occurrence of postoperative infection at the operative site. If such an episode occurs, then it will be defined as=1 'YES' If such an episode does not occur, then it will be defined as=0 'NO'. Time Frame: 7 days postoperatively
 - Stenosis at the operative site. Occurrence of postoperative stenosis at the operative site. If such an episode occurs, then it will be defined as=1 'YES' If such an episode does not occur, then it will be defined as=0 'NO'. Time Frame: 7 days postoperatively
- Postoperative return to work time. Measurement unit: days. Time Frame: Postoperative period up to 1 month
- Complications occurring at 1 year postoperatively:
 - Pruritus. Occurrence of postoperative pruritus at the operative site. If such an episode occurs, then it will be defined as=1 'YES' If such an episode does not occur, then it will be defined as=0 'NO'. Time Frame: 1 year postoperatively
 - Mucosal proptosis. Occurrence of postoperative mucosal proptosis at the operative site. If such an episode occurs, then it will be defined as=1 'YES' If such an episode does not occur, then it will be defined as=0 'NO'. Time Frame: 1 year postoperatively
 - Perianal nodules. Occurrence of postoperative perianal nodules. If such an episode occurs, then it will be defined as=1 'YES' If such an episode does not occur, then it will be defined as=0 'NO'. Time Frame: 1 year postoperatively
 - Constipation. Occurrence of postoperative constipation. If such an episode occurs, then it will be defined as=1 'YES' If such an episode does not occur, then it will be defined as=0 'NO'. Time Frame: 1 year postoperatively
 - Tenesmus. Occurrence of tenesmus. If such an episode occurs, then it will be defined as=1 'YES' If such an episode does not occur, then it will be defined as=0 'NO'. Time Frame: 1 year postoperatively.

- Reoperation. Occurrence of reoperation. If the patient is reoperated, then it will be defined as=1 'YES' If the patient is not reoperated, then it will be defined as=0 'NO'. Time Frame: 1 year postoperatively
- Disease recurrence rate at 1 year postoperatively. Disease recurrence rate If such an episode occurs, then it will be defined as=1 'YES' If such an episode does not occur, then it will be defined as=0 'NO'. Time Frame: 1 year postoperatively
- Satisfaction level at 1 year postoperatively. Satisfaction level measured at a 0-10 scale. Time Frame: 1 year postoperatively
- Difference in the quality of life of the patient, at 1 month and 1 year postoperatively, compared to the respective preoperative measurements, based on the SF-36 questionnaire, weighted for the Greek²⁶. Time Frame: Preoperatively, 1 month postoperatively and 1 year postoperatively.

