3.12 Discharge Criteria

The patient will be discharged, when it is ensured that is medically safe to be released. In particular, as the exit time of the patient, will be regarded the time that the patient will fulfill the Clinical Discharge Criteria. More specifically, the patient should meet the following : steady vital signs, be oriented, without nausea or vomiting, mobilized with a steady gait, without a significant bleeding²⁸.

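### None of the six in-hospital adverse effects compared is specific to the second arm's sedation or nerve block, and unlisted events are not compared, so an overall claim of fewer adverse effects could be tilted towards that arm

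*Protocol*

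**What the plan says.** Each arm has its own anaesthetic. For the first arm (Protocol 3.4, SAP 4.4): "Prior to operation, the patients will be submitted to spinal anesthesia", with fentanyl in the spinal solution. For the second, experimental arm (Protocol 3.5, SAP 4.5): "Prior to operation, the patients will be submitted to pudendal nerve block", and then "Ten minutes before the operation, the patient will receive 1-2.5mg midazolam and 0.1-0.2 mg fentanyl".

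The endpoint "Difference in the rates of adverse effects during hospitalization" (Protocol 3.7, SAP 3.2) consists of six yes/no items: hypotension, nausea, vomiting, headache, urinary retention and bleeding at the operative site. Each is worded as a postoperative event, for example "Hypotension. Occurrence of postoperative hypotension", and is counted up to discharge, for at most 24 hours. The separate 7-day list holds only pain and four operative-site findings: oedema, hematoma, infection and stenosis.

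SAP 5.3 compares categorical variables by Pearson chi-square, with significance at p < 0.05. Neither document defines a total across the six items, a category for other events, or an analysis of events off the list. The data list in Protocol 3.11 is broader: it records adverse effects in general terms, and anaesthesia type.

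**The concern.** When two arms receive different anaesthetics, a fair comparison of in-hospital harm needs a place to count the harms of each. Here some items lean towards the first arm's anaesthetic, and none is particular to the second arm's. Respiratory depression or desaturation, excessive sedation or disorientation, a reaction to the local anaesthetic, and a block that fails and needs another technique have no item.

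Two things are at stake. A safety signal in the experimental arm could occur and still be missing from the adverse-effect comparison. And the endpoint's heading invites an overall reading (fewer adverse effects with the new technique), which six items chosen in this way may not support.

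**Working it through.** **1. Items against regimens.** The documents attribute no listed effect to either anaesthetic. The mapping below is general clinical knowledge and is used as an assumption.

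| Item | Where it can arise |
|---|---|
| Headache | leans towards spinal anaesthesia |
| Urinary retention | partly spinal anaesthesia, partly anorectal surgery in either arm |
| Hypotension, nausea, vomiting | either arm |
| Operative-site bleeding | surgical, either arm |
| Any item specific to sedation or block | none |

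Three of the six items can therefore register second-arm sedation effects, one or two lean towards the first arm, and none leans towards the second.

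**2. The planned tests.** Each item is compared separately. The counted rate of headache, say, depends only on headaches in each arm, so an unlisted event does not change it. The false-positive rate of the six planned tests is not inflated by this gap.

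**3. A signal that would not be shown.** The plan has 30 patients per arm. That figure reproduces: (1.96 + 0.8416)² × (0.725 × 0.275 + 0.90 × 0.10) / (0.175 + 0.10)² = 7.849 × 0.289375 / 0.075625 = 30.03, or 31 when rounded up. It serves here only as an input. If an unlisted harm has true rate r, the chance of at least one case among 30 is 1 − (1 − r)³⁰. For assumed r of 1%, 2%, 5% and 10% this is 26%, 45%, 79% and 96%. None of these cases would enter the adverse-effect comparison.

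**4. A pooled total (not planned; illustration only).** Suppose both arms have the same true rate p of any harm, and shares m₁ and m₂ of the events fall outside the list. The counted rates are p(1 − m₁) and p(1 − m₂), and the spurious difference is p(m₂ − m₁). The chance of a false advantage for the second arm is the sum of the two binomial probabilities (n = 30 each) over all outcomes in which the first arm has more events and the uncorrected chi-square exceeds 3.841. All values of p, m₁ and m₂ are assumptions.

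| p | m₁ | m₂ | Spurious difference | False advantage |
|---|---|---|---|---|
| 10% | 0 | 30% to 80% | 3 to 8 points | 6.1% to 21.8% |
| 20% | 0 | 30% to 80% | 6 to 16 points | 8.8% to 52.7% |
| 30% | 0 | 30% to 80% | 9 to 24 points | 12.0% to 72.1% |
| 10%, 20%, 30% | 30% | 50% | 2, 4, 6 points | 3.9%, 7.3%, 8.5% |
| 10%, 20%, 30% | 30% | 30% | 0 | 2.2%, 2.7%, 2.4% |
| 10%, 20%, 30% | 0 | 0 | 0 | 2.7%, 2.5%, 2.4% |

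The result is driven by the gap between m₁ and m₂, on which the documents are silent.

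**The case against.** A reader might infer that the list is closed, that second-arm harms cannot be recorded at all, and that the comparison therefore favours the experimental arm by construction. The documents do not support that, for these reasons:

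- Hypotension, nausea and vomiting can register sedation or opioid effects, and fentanyl is given in both arms: the spinal solution contains it too (Protocol 3.4).
- Protocol 3.11 records adverse effects without restriction. It also records anaesthesia type, which could reveal a change after a failed block.
- Discharge readiness under Protocol 3.12 requires "steady vital signs, be oriented, without nausea or vomiting, mobilized with a steady gait". The time at which this is met is itself a secondary endpoint, so lasting disorientation or unstable vital signs would lengthen it. Over-sedation could likewise delay mobilization, another secondary endpoint.
- The list misses first-arm harms as well. Hypotension during surgery and headache after 24 hours are outside the window, and a failed spinal has no item.
- No composite is planned, so the larger percentages above describe an analysis that the trial does not specify, with nothing missed in the first arm.

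All of this stands, and it rules out a claim of built-in bias of known size. It does not close the gap. Recording an event is not comparing it, and neither document compares events off the list. A longer discharge time does not tell a reader that a sedation harm occurred.

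**Conclusion.** The point holds as a limited one. The compared list has no item specific to the second arm's sedation or block, and nothing beyond the list is compared. The item-by-item results can be taken at face value for the effects they name. What they cannot carry is an overall statement that the second arm has fewer adverse effects, because such a statement could be tilted towards that arm. A sedation or block signal would show only indirectly, through discharge or mobilization time.

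Direction and size are not established. They depend on event rates and on the share missed in each arm, and the documents give neither. The 6% to 72% range applies only to a pooled total with no first-arm events missed, and it falls to about nominal when both arms miss 30%. The mapping of items to anaesthetics is itself an assumption. The primary endpoint and the sample size are unaffected. This is a cheap improvement to a secondary safety comparison.

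**What to change.** In Protocol 3.7 and SAP 3.2:

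- Add yes/no items, recorded identically in both arms: respiratory depression or desaturation; excessive sedation or disorientation; local-anaesthetic reaction; and inadequate anaesthesia, spinal or block, needing another technique.
- Count these from the start of anaesthesia to discharge. Sedation and block are given before surgery, so items limited to the postoperative period would miss many of the events they are meant to catch.
- Add a field for any other adverse effect, and one summary endpoint: any adverse effect from the start of anaesthesia to discharge, listed or not.
- Base any overall safety statement on that summary, and attribute a difference to the package of technique plus anaesthesia, not to the surgical technique alone.

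If the list stays as it is, state in the SAP that the six items do not support a claim of fewer adverse effects overall.

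The cost is a few extra fields, which should be obtainable from the anaesthetic record and patient chart, some added wording, and a few more rare-event results to report. No extra patients or visits are needed, and no change to the anaesthetics or to clinical management is proposed.

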3.13 Follow up

One week after the operation, the patient will be summoned to reply for any postoperative complications, the return to work time, and the current pain level. One month postoperatively, the patient will be asked about the remission of the symptoms. One year after the operation, the patient will be examined for disease recurrence and will be asked about the overall satisfaction regarding the operation.

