4.6 Covariates

The following data will be considered as covariates

- Demographics (Gender, Age, Weight, Height, ASA)
- Symptoms (Proptosis, Bleeding, Pruritus, Pain)
- Hemorrhoid Grade

5. Statistical Methodology

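### Operative-site bleeding is counted only until discharge (24 h at most) and wound complications only at 7 days, so later events have no dedicated endpoint and bleeding observation time can differ by arm

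*Protocol*

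**What the plan says.** Protocol 3.7 and SAP 3.2 give the same endpoint list. Bleeding appears once, among the adverse effects during hospitalization: "Bleeding at the operative site. Occurrence of postoperative bleeding at the operative site", with "Time Frame: Postoperative period up to hospital discharge. Maximum time frame 24 hours". The time at which the patient can be safely discharged is a separate secondary endpoint with a longer limit: "Time Frame: Postoperative period up to hospital discharge. Maximum time frame 48 hours".

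Under "Complications occurring at 7 days postoperatively" the list has pain, oedema, hematoma, infection and stenosis. Under "Complications occurring at 1 year postoperatively" it has pruritus, mucosal proptosis, perianal nodules, constipation, tenesmus and reoperation. Disease recurrence at 1 year is listed separately.

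Protocol 3.13 describes the contacts. At one week there is an open question on postoperative complications. For the next contact it says: "One month postoperatively, the patient will be asked about the remission of the symptoms". At one year the patient is examined for recurrence and asked about satisfaction. SF-36 is also due at 1 month and 1 year (Protocol 3.7 and 3.11). Protocol 3.12 makes absence of significant bleeding a condition for discharge.

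Bleeding is a symptom of the disease under study. Protocol 2.1 states: "Symptomatic hemorrhoids, includes bleeding, pruritus, pain, poor hygiene and the presence of palpable hemorrhoid nodules". SAP 4.6 also names it among the baseline symptoms used as covariates.

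**The concern.** Both arms ligate hemorrhoidal arteries, so bleeding is a natural safety outcome for comparing them. As written, the only bleeding comparison covers the hospital stay, and it stops when patients have been judged free of significant bleeding. Bleeding at home would not be counted under its own name, and neither would an infection or hematoma arising after day 7.

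The window is also not fixed. It closes at discharge or at 24 h, whichever comes first. The Doppler arm has spinal anesthesia and the experimental arm has pudendal nerve block with sedation (Protocol 3.4 and 3.5), so discharge may well come at different times. An arm discharged earlier is watched for less time and may show fewer bleeds for that reason alone. A report of no difference in bleeding could then be read as a safety finding about the techniques when it describes a short window that may be unequal.

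**Working it through.** **1. The plan's own figure.** Protocol 3.8 gives 30 per group from remission rates of 72.5% and 90%, a 10-point margin, alpha 2.5% (taken as one-sided) and 80% power (printed as beta).

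n = [p1(1−p1) + p2(1−p2)] × (z0.975 + z0.80)² / (p2 − p1 + margin)²

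= (0.199375 + 0.09) × (1.960 + 0.842)² / 0.275² = 30.03

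The stated 30 gives 79.96% power, so it reproduces. It depends only on 1-month remission, and changing the bleeding or complication windows does not touch it.

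**2. Coverage by time point (Protocol 3.7, identical in SAP 3.2).**

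| Item | To discharge, max 24 h | 7 days | 1 month | 1 year |
|---|---|---|---|---|
| Operative-site bleeding | yes | – | – | – |
| Hematoma, infection, oedema, stenosis | – | yes | – | – |
| Symptom remission (primary) | – | – | yes | – |
| Reoperation | – | – | – | yes |
| Disease recurrence | – | – | – | yes |

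No named complication item covers day 7 to 1 month. The 7-day heading can also be read in two ways: present on day 7, or occurring at any time up to it.

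**3. What the indirect routes can carry.**
- Remission at 1 month is a single yes/no. Ongoing bleeding can make it NO, but a bleed that has resolved by then could still score YES.
- Hematoma at 7 days may reflect some bleeding, but not external bleeding as such.
- Recurrence at 1 year is not defined by component.
- Reoperation captures only events that led to surgery. After day 7 it is the only listed item that could reflect an infection.
- The one-week question can elicit a bleed, but no named 7-day endpoint receives the answer.

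**4. Observation time.** For a patient with discharge time D, the chance of a counted bleed is F(min(D, 24 h)), where F(t) is the probability of a bleed by time t. If D differs between arms, the counted proportions can differ even when F is the same in both. If D exceeds 24 h, in-hospital bleeding after 24 h is not counted. In the group's own Doppler-guided series (Protocol 2.2), 64.4% were discharged within 24 h. If that held in the Doppler arm, 35.6% × 30 = 10.7, or about 11 patients, would still be in hospital after the bleeding window closed. The other 19 or so would have windows of up to 24 h, ending at discharge. No corresponding figure is given for the experimental arm.

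**5. Scale of late events.** The documents give no rate, so these are assumed. Expected number per arm = 30p, and chance of at least one = 1 − (1 − p)^30.

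| Assumed late-event rate | Expected per arm | At least one in 30 |
|---|---|---|
| 1% | 0.3 | 26% |
| 2% | 0.6 | 45% |
| 5% | 1.5 | 79% |
| 10% | 3.0 | 96% |

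**6. What the added data could show.** Zero events in 30 leaves a one-sided 95% upper limit of 1 − 0.05^(1/30) = 9.5%. Power of a two-sided 5% test with 30 per arm (normal approximation, pooled variance under the null) is about 25% for 5% versus 15% and 42% for 5% versus 20%. The items would support description, not a formal comparison.

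**The case against.** The strongest reply is that later bleeding is not lost. Bleeding is a hemorrhoid symptom in both documents, so a patient still bleeding at 1 month can be scored as not in remission in the primary comparison. Recurrence is examined at 1 year, and reoperation has no restriction by cause. The one-week contact asks about any complication, and Protocol 3.11 records 7-day complications without limiting them to the five listed. This stands, and it rules out a stronger reading that a reader might infer: that bleeding after discharge, or infection after day 7, never enters the comparison of the techniques. What the routes do not provide is a count of bleeding as such over the same period in both arms.

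It can also be said that the item sits under in-hospital adverse effects, so an accurate report would carry that label, and that 30 patients per arm could not compare late bleeding formally. Both are fair. They limit what the addition can deliver, but they do not supply the missing safety description.

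Protocol 2.1 cites a meta-analysis in which hemorrhoidal artery ligation did better on postoperative bleeding, but it states no comparator or time window there. It is not evidence that late bleeding differs between these two techniques, and the point does not rest on it.

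**Conclusion.** The point holds in a limited form. Bleeding after discharge or 24 h, and wound complications after day 7, have no dedicated endpoint and are captured only indirectly. The bleeding window depends on discharge time, so observation can differ by arm, and it closes at 24 h although time to safe discharge runs to 48 h. The coverage gap follows from the text alone. A difference in discharge time between arms is a plausible consequence of the different anesthesia, but the documents do not show one.

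The number of events affected cannot be derived from the documents. At assumed late-bleeding rates of 1% to 10% it is 0.3 to 3 patients per arm, and some of these would surface through the indirect routes. A reader might also be tempted to size the gap as one day out of the whole follow-up. That is a share of calendar time, not of bleeding risk, and the documents give nothing to convert one into the other.

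The sample size and the primary analysis are unaffected. This is a low-cost improvement to the safety comparison and does not threaten the main conclusion.

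**What to change.** Make these changes in Protocol 3.7, 3.11 and 3.13 and in SAP 3.2:

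- Add a yes/no item, bleeding at the operative site at any time since surgery, at the existing 7-day and 1-month contacts, so that both arms share fixed windows that do not depend on discharge.
- Ask infection and hematoma again at 1 month, and state whether the 7-day items mean present on day 7 or at any time up to it.
- Add bleeding to the 1-year list.
- Label the existing item as in-hospital bleeding only, and reconcile its 24 h cap with the 48 h limit for time to safe discharge.
- In the SAP, report these items as counts and percentages by arm with confidence intervals, described as descriptive.

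Items on unplanned visits or readmission since the last contact would be useful but are optional.

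The cost is a few yes/no questions at contacts already scheduled, plus wording in the protocol, SAP and case report form. No visit is added and the sample size does not change. The downside is a longer secondary list with items that 30 patients per arm cannot compare with good power.
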